# 5.4.8. Pharmacokinetic and Concomitant Medication Samples Associated with Safety Signals

If needed, a summary listing will be created to align additional PK and concomitant medication samples temporally surrounding an untoward safety signal, such as and AESI, SAE, QTc prolongation, or withdrawal for safety reasons.

#### 5.5. EXTENSION PHASE

Patients enrolled in the 40-week open-label extension phase will receive either MIN-101 32 mg or 64 mg. As described in section 3.2, patients who received placebo in the double-blind 12-week treatment phase will be randomized (at Baseline) to receive one of the two MIN-101 doses at the conclusion of the double-blind phase. To evaluate longer-term efficacy and safety effects, cumulative data from all patients enrolled in the 40-week extension phase (through the entire 52-week study period) will be summarized descriptively and/or graphically, as appropriate, by visit and treatment arm sequence using the following groups:

- Placebo to MIN-101 32 mg
- Placebo to MIN-101 64 mg
- Placebo to MIN-101 Total
- MIN-101 with 3 sub-headers
  - o 32 mg
  - 64 mg
  - o Total (all MIN-101 from the outset)
- Overall

The "overall" column will be used for demographic and patient characteristics data summaries, as appropriate.

Changes from Baseline for the patients treated with placebo that crossed-over to MIN-101 doses will be presented twice, based on Baseline being defined as the original study Baseline (Visit 3) and as the last assessment on placebo at Week 12 (Visit 11), as appropriate.

Efficacy trends in the extension phase, including relapses, will be presented in the ITT population only.

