## 1.4.2.3. Safety

MIN-101 was generally well-tolerated. The most common treatment-emergent adverse events (TEAEs) were headache, insomnia, agitation, somnolence, nausea, anxiety, and worsening of schizophrenia symptoms. No postural hypotension was reported. MIN-101 did not induce any

significant change in safety laboratory parameters nor in prolactin levels. The incidence of extrapyramidal symptoms with MIN-101 was low and similar to that observed with placebo. Mean change in body weight was similar with MIN-101 and placebo. No deaths and no instances of Torsade de Pointes, seizures or myocardial ischemia were reported in patient studies

In study MT-210-A02, 50% of patients in the MIN-101 and placebo treatment groups had at least 1 TEAE. Half of the patients who reported TEAEs had events considered possibly or probably related to study drug. The most common TEAEs in the MIN-101 treatment group were headache, dizziness, and nausea. There were no severe TEAEs. A total of 3 patients in the MIN-101 treatment group and 1 patient in the placebo treatment group discontinued due to an AE occurrence. All 3 patients, regardless of treatment, discontinued for mild to moderate prolongation of QTc intervals and/or tachycardia.

In study CYR-101C01, 62.5% of patients receiving placebo and 68.1% of patients receiving MIN-101 reported at least 1 TEAE. Most of the reported TEAEs were classified as unrelated or unlikely related to the study treatment.

The System Organ Class most commonly affected by TEAEs were psychiatric disorders (placebo 45.8% patients; MIN-101: 46.8% patients), followed by gastrointestinal disorders and nervous system disorders. The TEAEs most commonly reported were: nausea, somnolence, agitation, anxiety, insomnia, and schizophrenia.

The majority of TEAEs were mild or moderate in intensity. There were 17 severe TEAEs, 11 of which occurred in the MIN-101 group and 6 in the placebo group. All were classified in the System Organ Class of psychiatric disorders: agitation, anxiety, depression, hostility, negativism, restlessness, schizophrenia, suicide attempt, and tension.

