# 10.10. Extension Phase

Patients enrolled in the 40-week open-label extension phase will receive either MIN-101 64 mg or 32 mg. Patients who received placebo in the double-blind 12-week treatment phase will be randomized on Day 1 (Visit 4) to receive one of the two MIN-101 doses. Data from all patients enrolled in the 40-week extension phase will be summarized descriptively, as appropriate, by treatment arm sequence (MIN-101 64 mg, MIN-101 32 mg, placebo to MIN-101 64 mg, placebo to MIN-101 32 mg, overall MIN-101, overall placebo to MIN-101, and overall) as appropriate, and by visit.

All data from the 40-week extension phase will be analyzed separately upon last patient enrolled in this study has Visit 27 assessments. Change from Baseline data for the patients treated with placebo and crossed-over to MIN-101 doses will be presented twice, based on Baseline being defined as the original study Baseline (Visit 3) and as the last assessment on placebo at Week 12 (Visit 11), as appropriate.

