### Last Dose of Study Drug (Open-Label Extension Phase)

Last Dose of Study Drug (Open-Label Extension Phase) is defined as the last date a patient received study drug through the end of the open label extension phase (up to Week 52). If a patient discontinued drug during the 12-week double-blind phase, the last dose of study drug for the open label extension would be the last dose of study drug in the double-blind phase.

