## 4.3. SAFETY POPULATION (SAF)

The safety population is the population of all patients who were randomly assigned to study drug and received at least one dose of study treatment. Patients in this population will be analyzed according to the treatment they received, regardless of which treatment they were randomly assigned. All safety and tolerability analyses will be based on this population and treatment assignment.

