#### 5.4. SAFETY ANALYSES

Safety and tolerability will be analyzed for the double-blind treatment phase using the Safety Population and will be repeated for the whole study. Safety assessments include adverse events (AEs), clinical laboratory parameters, vital signs including body weight and waist circumference, ECG parameters, physical examination, Abnormal Involuntary Movement Scale (AIMS), Barnes

Akathisia Rating Scale (BARS), S-AS, and the Sheehan Suicidality Tracking Scale (Sheehan-STS), and the Readiness for Discharge Questionnaire (RDQ).

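### The 52-week safety tables count placebo-period events under Placebo to MIN-101, and SAP 5.5 disagrees with SAP 5.4 and 9.2 on which patients are counted

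*SAP*

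**What the plan says.** SAP 5.5 sets out the long-term summary. It covers "cumulative data from all patients enrolled in the 40-week extension phase (through the entire 52-week study period" and is shown by visit and treatment sequence. The columns are Placebo to MIN-101 (32 mg, 64 mg, total) and, separately, MIN-101 32 mg, 64 mg and "Total (all MIN-101 from the outset". The Overall column is kept for demographics and patient characteristics. Change from Baseline in crossover patients is shown twice, against Visit 3 and against Visit 11. Protocol 10.10 uses the same set of patients: "Data from all patients enrolled in the 40-week extension phase will be summarized descriptively".

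The definition of a treatment-emergent adverse event in SAP 3.3.8 runs from the start of study treatment to 14 days after the last dose. It does not distinguish placebo from MIN-101.

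On who is counted, SAP 5.4 says: "Safety and tolerability will be analyzed for the double-blind treatment phase using the Safety Population and will be repeated for the whole study". SAP 4.3 defines that population as "all patients who were randomly assigned to study drug and received at least one dose of study treatment", with no requirement to enter the extension. The extension safety tables in SAP 9.2 list Safety as their population. SAP 3.3.8 also covers patients who stopped early: "If a patient discontinued drug during the 12-week double-blind phase, the last dose of study drug for the open label extension would be" their last double-blind dose.

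**The concern.** Protocol 3.2 gives long-term safety as one purpose of the extension. Protocol 3.2 also has every patient hospitalised again at Week 12, so that former placebo patients are closely observed when they first take MIN-101. As the SAP stands, no adverse-event column isolates that first exposure. A crossover patient with an event in Week 3 on placebo is counted under a heading that names MIN-101. SAP 5.4.1 keeps the greatest severity per preferred term, so a severe event on placebo would also hide a mild recurrence on drug.

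The population conflict matters for a different reason. Patients who reach the extension have already got through 12 weeks of treatment. Protocol 1.5 says that the two Phase 2b patients with a significant QTcF increase on 64 mg were found within the first 4 weeks. A long-term column limited to extension entrants would leave out patients of that kind who were withdrawn.

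**Working it through.** **Exposure.** Protocol Table 3 gives 84 tablets for the double-blind phase and 280 for the extension. At one tablet a day, 12 × 7 = 84, 40 × 7 = 280, and 84 + 280 = 364, so the table reproduces. Placebo time in the crossover columns is 84/364 = 23.1%. In the from-the-outset columns it is 0%.

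**Arm sizes.** The 2:2:1:1 allocation of 501 in SAP 3.2 gives 334 patients on MIN-101 from the outset and 167 on placebo.

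**Which displays are affected.**
- Adverse events (SAP 5.4.1): affected. They are counts of patients and events from the start of study treatment.
- Potentially clinically significant laboratory and ECG values on absolute criteria (SAP 5.4.2, 5.4.5): affected where any post-Baseline occurrence is counted.
- Potentially clinically significant vital signs: SAP 5.4.4 summarises them by time point, so they are affected only in an any-post-Baseline total.
- By-visit means: not affected. The windows in SAP Table 1 separate double-blind from open-label visits.
- QTcF increases of more than 30 or 60 msec: these are changes from Baseline, so the Visit 11 baseline arguably covers them.

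**Direction and size in percent-of-patients tables.** Let M be the true 40-week incidence on drug and P the 12-week incidence on placebo, taken as independent. The displayed proportion is 1 − (1 − M)(1 − P). With M = 10% (assumed):
- P = 2%: 11.8%
- P = 5%: 14.5%
- P = 10%: 19.0%

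The displayed figure cannot fall below M.

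**Illustration for any adverse event.** Protocol Table 2 reports that 165 of 244 Phase 2b patients completed the double-blind phase. Applied here, 167 × 165/244 = 113 crossovers. Protocol 1.4.2.3 reports for Phase 2a that "62.5% of patients receiving placebo" had at least one event, so 113 × 0.625 = 71 would already be counted before any MIN-101 dose. At an assumed 50% the number is 56. The 62.5% comes from all placebo patients in another trial, not from completers, so this is a rough guide only.

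**Entrants-only reading.** MIN-101 patients missing from the from-the-outset columns = 334 × non-entry rate:
- Phase 2b, 79/244 = 32.4%: 108
- assumed 20%: 67
- assumed 40%: 134

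The Phase 2b rate pools all arms and measures completion, not entry to an extension. The 40% in the sample-size section is a different quantity: it concerns missing efficacy assessments.

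**Safety Population reading.** No MIN-101 patient is missing. But about 167 × 79/244 = 54 placebo patients would never take MIN-101, and SAP 5.5 has no column for them. Each was assigned an open-label dose at randomisation, so they could fall into the Placebo to MIN-101 denominators by default. An event absent on placebo with a true on-drug incidence of 10% would then show as 113 × 0.10 / 167 = 6.8%.

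**The case against.** A reader might infer that long-term MIN-101 risk is diluted throughout and that early withdrawals disappear. The documents do not support either.

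On dilution, SAP 5.4.1 plans counts of patients and events and no person-time rates. Added placebo events can only raise a crossover percentage or leave it unchanged. A rate per patient-year would be pulled down, to (12 × 0 + 40m)/52 = 77% of the true on-drug rate m if the placebo rate were zero, but no such rate is planned. The from-the-outset columns hold no placebo time and are not pooled with the crossovers. The one route to dilution is the denominator question under the Safety Population reading, which the SAP leaves open.

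On withdrawals, SAP 5.4, SAP 4.3, the population listed in SAP 9.2 and the last-dose rule in SAP 3.3.8 all point to keeping every dosed patient. The double-blind tables in SAP 9.1 report them, and SAP 5.4.1 lists deaths, discontinuations due to events and serious events separately. The figure of 108 therefore holds only if the SAP 5.5 wording is followed literally.

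It could also be said that SAP 4.3 already analyses patients by treatment received. That rule classifies patients, not events, and a crossover patient received both treatments. Finally, exposure-adjusted rates are a preference and their absence is not an error. These points narrow the concern. They do not supply the attribution rule or settle the population.

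**Conclusion.** Two defects stand. First, SAP 5.5 read with the treatment-emergent definition puts placebo-period adverse events and absolute-value outliers into the cumulative Placebo to MIN-101 columns. The contamination is usually upward, and its size depends on background incidence: small for rare events, large for any adverse event. Second, SAP 5.5 conflicts with SAP 5.4 and 9.2 on who is counted. Under the entrants-only wording, roughly a third of the MIN-101 patients would be absent from the from-the-outset columns, if Phase 2b completion is a fair guide to extension entry.

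The primary and key secondary efficacy analyses are not touched, and the double-blind safety tables are sound on this point. The crossover columns of the long-term safety tables cannot be read as on-drug incidence until this is settled, so it should be changed before the final database lock.

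**What to change.** In the extension safety tables, count events and outliers in crossover patients only from the first open-label dose. Their placebo-period events stay in the double-blind tables.

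State one population for the MIN-101 columns: all Safety Population patients with at least one MIN-101 dose, including those withdrawn in the double-blind phase, followed from the first MIN-101 dose to 14 days after the last, by dose. State also that placebo patients who never received MIN-101 are not in the Placebo to MIN-101 denominators. Align SAP 5.5 with SAP 5.4 and 9.2 accordingly.

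Exposure-adjusted rates would be a useful but optional addition, since follow-up differs between crossovers and patients on MIN-101 from the outset.

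The cost is SAP wording and a set of re-run tables. No new data are needed.

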## 6. MAJOR PROTOCOL VIOLATIONS

Possible major protocol deviations will be identified and displayed in a summary table as well as a data listing and sorted by patient and study day (where applicable). The following deviations may be identified as major protocol deviations from the database:

- Violations of inclusion/exclusion criteria that could interfere with efficacy results, such as erroneous diagnosis
- Poor compliance with study drug (<75%)
- Intake of prohibited concomitant medication

## 7. CHANGES IN THE PLANNED ANALYSES

Relative to the protocol for MIN-101C07.v1.0, Amendment 2, dated 26 September 2018, there is a change in the conduct of the analysis. For the analyses planned for the EMA dossier, a multiple imputation approach will be used to impute values for missing primary (12-week NSFS) and key secondary (12-week PSP total score) endpoint data. Additionally, the PK/PD analysis discussed in the protocol will be part of the population PK analysis and reporting of the integrated data across multiple protocol, and a new PK/PD analyses were introduced in the Statistical Analysis Plan (SAP) to address exposure-response relationships, as outlined in Section 5.3.2.

Otherwise, the efficacy analyses were expanded from the protocol statistical plan but without additional deviations in the conduct of the study or the planned analysis being anticipated. Should any deviations from the analyses specified in the authorized SAP arise, such deviations will be documented in the final clinical study report.

## 8. PROGRAMMING CONVENTIONS

- Page orientation, margins, and fonts: Summary tables, listings, and figures will appear in landscape orientation. There should be a minimum of a 1.25" boundary on the upper (bound) edge, and a minimum of a 1.0" boundary on the remaining three edges. Output should be printed in Courier New with a point size of 8. Titles may be printed using a larger font (e.g., Arial point size 10).
- Identification of analysis population: Every summary table and figure should clearly specify the analysis population being summarized. Listings will be prepared for all patients.
- Group headers: In the summary tables, the group headers will identify the summary group and
  the sample size for the indicated analysis population. Of note, the header's sample size does
  not necessarily equal the number of patients actually summarized within any given summary
  module; some patients in the analysis population may have missing values and thus may not
  be summarized.
- Suppression of percentages corresponding to null categories: When count data are presented as category frequencies and corresponding percentages, the percent should be suppressed when the count is zero in order to draw attention to the non-zero counts.
- Presentation of sample sizes: Summary modules should indicate, in one way or another, the
  number of patients actually contributing to the summary statistics presented in any given
  summary module. As mentioned above, this may be less than the number of patients in the
  analysis population due to missing data.
  - In the quantitative modules describing continuous variables (and thus presenting sample size, means, and standard deviations), the sample size should be the number of non-missing observations. The number of missing observations, if any, will be noted.
  - For categorical variables that are presented in frequency tables, the module should present the total count in addition to the count in each category. Percentages should be calculated using this total as the denominator, and the percentage corresponding to the sum itself (that is, 100%) should be presented so as to indicate clearly to a reviewer the method of calculation. The number of missing observations, if any, will be noted.
- Sorting: Listings will be sorted by treatment group, patient number and date, if applicable. If a listing is sorted in a different manner, a footnote will indicate as such.
- General formatting rules: Rounding for all variables will occur only as the last step, immediately prior to presentation in listings, tables, and figures. No intermediate rounding will be performed on derived variables. The standard rounding practice of rounding numbers ending in 0-4 down and numbers ending in 5-9 up will be employed.
- The presentation of numerical values will adhere to the following guidelines:
  - Raw measurements will be reported to the number of significant digits as captured electronically or on the CRFs.
  - Standard deviations will be reported to one decimal place beyond the number of decimal places the original parameter is presented.

- Means will be reported to the same number of significant digits as the parameter.
- Dates will be formatted as DDMMMYYYY. Partial dates will be presented on data listings as recorded on CRFs.
  - Time will be presented according to the 24-hour clock (HH:MM).

## 9. PROPOSED TABLES, LISTINGS, AND FIGURES

## 9.1. ANALYSIS OF DOUBLE-BLIND PHASE

Item	Number	Description	Population		
Accountabilit	Accountability and Baseline Characteristics				
Table	14.1.1	Patient Disposition	Enrolled		
Table	14.1.2	Protocol Deviations	ITT		
Table	14.1.3	Analysis Sets	Enrolled		
Table	14.1.4.1	Demographics and Disease Characteristics at Baseline	ITT		
Table	14.1.4.2	Demographics and Disease Characteristics at Baseline	PP		
Table	14.1.5	Medical History	ITT		
Table	14.1.6	Study Drug Exposure and Compliance	Safety		
Table	14.1.7	Concomitant Medications by ATC Classification and Preferred Term	Safety		
Efficacy	•				

Item	Number	Description	Population
		Personal and Social Performance (PSP) Score, by Visit	ITT
Table	14.2.2.1.3	Summary and Change from Baseline in Personal and Social Performance (PSP) Score, by Visit	PP
Table	14.2.2.2.1	Summary and Change from Baseline in Personal and Social Performance (PSP) Score, by Visit, Age Subgroup Analysis	ITT
Table	14.2.2.3.1	Summary and Change from Baseline in Personal and Social Performance (PSP) Score, by Visit, BMI Subgroup Analysis	ITT
Table	14.2.2.4.1	Summary and Change from Baseline in Personal and Social Performance (PSP) Score, by Visit, Antipsychotic Medication History Subgroup Analysis	ITT
Table	14.2.2.5.1	Summary and Change from Baseline in Personal and Social Performance (PSP) Score, by Visit, 01 February 2020 Cutoff Analysis	ITT
Table	14.2.2.6.1	Summary and Change from Baseline in Personal and Social Performance (PSP) Score, by Visit,	ITT
Table	14.2.2.6.2	Summary and Change from Baseline in Personal and Social Performance (PSP) Score, by Visit,	

Item	Number	Description	Population
Table	14.2.4.1		
		and Social Performance (PSP) Subscale Scores, by Visit	ITT
Table	14.2.6.2	Summary and Change from Baseline in Personal and Social Performance (PSP) Subscale Scores, by Visit	PP
Table	14.2.7.1	Summary and Change from Baseline in Clinical Global Impression of Severity (CGI-S) Score, by Visit	ITT
Table	14.2.7.2	Summary and Change from Baseline in Clinical Global Impression of Severity (CGI-S) Score, by Visit	PP
Table	14.2.8.1		

Item	Number	Description	Population
Table	14.2.12.2		PP
	kinetics and Pharn		
Table	14.2.13.1	Plasma Concentrations of MIN-101, by Visit	ITT (with PK)
Table	14.2.13.2	Plasma Concentrations of MIN-101 Metabolite BFB-520, by Visit	ITT (with PK)
Table	14.2.14.1.1.1	Effect of Plasma concentration exposure of MIN-101 on Change from Baseline in PANSS Total Score	ITT (with PK)
Table	14.2.14.1.1.3	Effect of Plasma concentration exposure of MIN-101 on Change from Baseline in PANSS Total Score	PP (with PK)
Table	14.2.14.1.2.1	Effect of Plasma concentration exposure of BFB-520 on Change from Baseline in PANSS Total Score	ITT (with PK)
Table	14.2.14.1.2.3	Effect of Plasma concentration exposure of BFB-520 on Change from Baseline in PANSS Total Score	PP (with PK)
Table	14.2.14.2.1.1	Effect of Plasma concentration exposure of MIN-101 on Change from Baseline in Marder Negative Symptoms Factor Score (NSFS)	ITT (with PK)
Table	14.2.14.2.1.3	Effect of Plasma concentration exposure of MIN-101 on Change from Baseline in Marder Negative Symptoms Factor Score (NSFS)	PP (with PK)
Table	14.2.14.2.2.1	Effect of Plasma concentration exposure of BFB-520 on Change from Baseline in Marder Negative Symptoms Factor Score (NSFS)	ITT (with PK)
Table	14.2.14.2.2.3	Effect of Plasma concentration exposure of BFB-520 on Change from Baseline in Marder Negative Symptoms Factor Score (NSFS)	PP (with PK)
Table	14.2.14.3.1.1	Effect of Plasma concentration exposure of MIN-101 on Change from Baseline in PANSS Subscale Scores	ITT (with PK)
Table	14.2.14.3.1.3	Effect of Plasma concentration exposure of MIN-101 on Change from Baseline in PANSS Subscale Scores	PP (with PK)
Table	14.2.14.3.2.1	Effect of Plasma concentration exposure of BFB-520 on Change from Baseline in PANSS Subscale Scores	ITT (with PK)
Table	14.2.14.3.2.3	Effect of Plasma concentration exposure of BFB-520 on Change from Baseline in PANSS Subscale Scores	PP (with PK)
Table	14.2.14.4.1.1	Effect of Plasma concentration exposure of MIN-101 on Change from Baseline in Marder Factor Scores	ITT (with PK)
Table	14.2.14.4.1.3	Effect of Plasma concentration exposure of MIN-101 on Change from Baseline in Marder Factor Scores	PP (with PK)

Item	Number	Description	Population
Table	14.2.14.4.2.1	Effect of Plasma concentration exposure of BFB-520 on Change from Baseline in Marder Factor Scores	ITT (with PK)
Table	14.2.14.4.2.3	Effect of Plasma concentration exposure of BFB-520 on Change from Baseline in Marder Factor Scores	PP (with PK)
Safety			
Table	14.3.1.1.1	Summary of Adverse Events	Safety
Table	14.3.1.1.2	Summary of Adverse Events, 01 February 2020 Cutoff	Safety
Table	14.3.1.2.1	Treatment-Emergent Adverse Events by System Organ Classification, Preferred Term and Maximum Severity	Safety
Table	14.3.1.2.2	Treatment-Emergent Adverse Events by System Organ Classification, Preferred Term and Maximum Severity, 01 February 2020 Cutoff	Safety
Table	14.3.1.3.1	Treatment-Emergent Adverse Events Related to Study Treatment by System Organ Classification, Preferred Term and Maximum Severity	Safety
Table	14.3.1.3.2	Treatment-Emergent Adverse Events Related to Study Treatment by System Organ Classification, Preferred Term and Maximum Severity, 01 February 2020 Cutoff	Safety
Table	14.3.1.4.1	Treatment-Emergent Adverse Events Leading to Discontinuation of Study Treatment by System Organ Classification, Preferred Term and Maximum Severity	Safety
Table	14.3.1.4.2	Treatment-Emergent Adverse Events Leading to Discontinuation of Study Treatment by System Organ Classification, Preferred Term and Maximum Severity, 01 February 2020 Cutoff	Safety
Table	14.3.1.5.1	Treatment-Emergent Fatal Adverse Events by System Organ Classification and Preferred Term	Safety
Table	14.3.1.5.2	Treatment-Emergent Fatal Adverse Events by System Organ Classification and Preferred Term, 01 February 2020 Cutoff	Safety
Table	14.3.1.6.1	Treatment-Emergent Serious Adverse Events by System Organ Classification and Preferred Term	Safety
Table	14.3.1.6.2	Treatment-Emergent Serious Adverse Events by System Organ Classification and Preferred Term, 01 February 2020 Cutoff	Safety
Table	14.3.1.7.1	Treatment-Emergent Adverse Events of Special Interest: Palpitations or Abnormal Heart Rhythms, Dizziness or Syncope, and Seizure	Safety

171111 101007	
Statistical Analysis	Plan

Item	Number	Description	Population
Table	14.3.1.7.2	Treatment-Emergent Adverse Events of Special Interest: Palpitations or Abnormal Heart Rhythms, Dizziness or Syncope, and Seizure, 01 February 2020 Cutoff	Safety
Table	14.3.4.1	Clinical Laboratory Hematology Parameters by Time Point	Safety
Table	14.3.4.2	Clinical Laboratory Chemistry Parameters by Time Point	Safety
Table	14.3.4.3	Clinical Laboratory Urinalysis Parameters (Continuous) by Time Point	Safety
Table	14.3.4.4	Clinical Laboratory Parameter Shifts from Baseline	Safety
Table	14.3.4.5	Potentially Clinically Significant Laboratory Values	Safety
Table	14.3.5.1	Vital Sign and Anthropomorphic Parameters and Changes from Baseline, by Time Point	Safety
Table	14.3.5.2.1	Potentially Clinically Significant Vital Signs Occurring Post-Baseline	Safety
Table	14.3.5.2.2	Vital Signs Parameter Shifts from Baseline	Safety
Table	14.3.5.3.1.1	ECG Parameters and Change from Baseline by Time Point	Safety
Table	14.3.5.3.1.2	ECG Parameters and Change from Baseline by Time Point, 01 February 2020 Cutoff	Safety
Table	14.3.5.3.2.1	QTcF (msec) Values and Change from Baseline Relative to Predefined Thresholds of Clinical Significance	Safety
Table	14.3.5.3.2.2	QTcF (msec) Values and Change from Baseline Relative to Predefined Thresholds of Clinical Significance, 01 February 2020 Cutoff	Safety
Table	14.3.5.3.3.1	Effect of Treatment Arm on Changes in QTcF using ANCOVA	Safety
Table	14.3.5.3.3.2	Effect of Treatment Arm on Changes in QTcF using ANCOVA, 01 February 2020 Cutoff	Safety
Table	14.3.5.3.4.1	Patients with Clinically Significant ECG Abnormalities Occurring Post-Baseline	Safety
Table	14.3.5.3.4.2	Patients with Clinically Significant ECG Abnormalities Occurring Post-Baseline, 01 February 2020 Cutoff	Safety
Table	14.3.5.3.5.1	Patients with Potentially Clinically Significant ECG Abnormalities Occurring Post-Baseline	Safety
Table	14.3.5.3.5.2	Patients with Potentially Clinically Significant ECG Abnormalities Occurring Post-Baseline, 01 February 2020 Cutoff	Safety
Table	14.3.5.3.5.3	ECG Parameter Shifts from Baseline	Safety

T. 1.1		Description	Population
Table	14.3.6.1	Summary and Change from Baseline in Abnormal Involuntary Movement Scale (AIMS) Composite Movement Score and Severity Index, by Visit	Safety
Table	14.3.6.2	Summary and Change from Baseline in Barnes Akathisia Rations Scale (BARS) and Global Clinical Assessment of Akathisia, by Visit	Safety
Table	14.3.6.3	Summary and Change from Baseline in Simpson- Angus Scale (S-AS) Score, by Visit	Safety
Table	14.3.6.4	Summary and Change from Baseline in Sheehan Suicidality Tracking Scale (STS) Subscores and Total Scale Score, by Visit	Safety
Listings	•		•
Listing	16.2.1	Patient Disposition	Enrolled
Listing	16.2.2.1	Protocol Deviations	ITT
Listing	16.2.2.2	Inclusion/Exclusion Criteria	Enrolled
Listing	16.2.3	Inclusion in Analysis Populations	Enrolled
Listing	16.2.4.1	Demographic and Baseline Characteristics	ITT
Listing	16.2.4.2	Psychiatric and Medical History	ITT
Listing	16.2.4.3	Schizophrenia Characteristics at Baseline	ITT
Listing	16.2.4.4	CYP2D6 Genotyping	Enrolled
Listing	16.2.4.5	Concomitant Medication Blood Sampling	Enrolled
Listing	16.2.4.6	Urine Drug and Alcohol Screening	Enrolled
Listing	16.2.4.7	Hospital Admissions and Discharge/Continuation	ITT
Listing	16.2.5.1	Study Drug Administration and Compliance	Safety
Listing	16.2.5.2	Prior and Concomitant Medications	Enrolled
Listing	16.2.5.3	Plasma Concentrations of MIN-101 and BFB-520	ITT (with PK)
Listing	16.2.6.1		ITT
Listing	16.2.6.2	Personal and Social Performance (PSP) Assessments	ITT
Listing	16.2.6.3	Clinical Global Impression of Severity (CGI-S) Assessments	ITT
Listing	16.2.6.4		
			ITT

	Number	Description	Population
Listing	16.2.7.1	Adverse Events	Enrolled
Listing	16.2.7.2	Treatment-Emergent Adverse Events	Enrolled
Listing	16.2.7.3	Adverse Events Leading to Discontinuation of Study Treatment	Enrolled
Listing	16.2.7.4	Fatal Adverse Events	Enrolled
Listing	16.2.7.5	Serious Adverse Events	Enrolled
Listing	16.2.7.6	Serious Adverse Events Occurring Prior to Randomization	Enrolled
Listing	16.2.7.7	Adverse Events for Subjects with Potentially Clinically Significant QTcF Values	Enrolled
Listing	16.2.7.8	Adverse Events for Subjects with Potentially Clinically Significant HR, QRS, or PR Values	Enrolled
Listing	16.2.7.9	Adverse Events of Special Interest	Enrolled
Listing	16.2.8.1.1	Laboratory Data – Chemistry	Enrolled
Listing	16.2.8.1.2	Laboratory Data – Hematology	Enrolled
Listing	16.2.8.1.3	Laboratory Data – Urinalysis	Enrolled
Listing	16.2.8.1.4	Laboratory Data - Serology	Enrolled
Listing	16.2.8.1.5	Laboratory Data – Serum Pregnancy Testing	Enrolled
Listing	16.2.8.1.6	Laboratory Results Outside Reference Range	Enrolled
Listing	16.2.8.1.7	Potentially Clinically Significant Laboratory Results	Enrolled
Listing	16.2.8.2.1	Vital Signs and Anthropomorphic Measures	Enrolled
Listing	16.2.8.2.2	Potentially Clinically Significant Vital Signs	Enrolled
Listing	16.2.8.3	Physical Examinations	Enrolled
Listing	16.2.8.4	12-Lead ECG Findings	Enrolled
Listing	16.2.8.5	Clinically Significant 12-Lead ECG Findings	Enrolled
Listing	16.2.8.6	Potentially Clinically Significant 12-Lead ECG Findings	Enrolled
Listing	16.2.8.6	Abnormal 12-Lead ECG Findings	Enrolled
Listing	16.2.9.1	Abnormal Involuntary Movement Scale (AIMS) Assessments	Enrolled
Listing	16.2.9.2	Barnes Akathisia Rating Scale (BARS) Assessments	Enrolled
Listing	16.2.9.3	Simpson-Angus Scale (S-AS) Assessments	Enrolled
Listing	16.2.9.4	Sheehan Suicidality Tracking Scale (STS) Assessments	Enrolled

Item	Number	Description	Population
Figures	•		
Figure	14.2.1.1.2		
			PP
Figure	14.2.2.1.2	Change from Baseline in Personal and Social Performance (PSP) Score using the Least Squares Means (±SE) from MMRM, by Visit	ITT
Figure	14.2.2.1.4	Change from Baseline in Personal and Social Performance (PSP) Score using the Least Squares Means (±SE) from MMRM, by Visit	PP
Figure	14.2.11.2	Time to Relapse in the Double-Blind Phase	ITT
Figure	14.2.11.4	Time to Relapse in the Double-Blind Phase	PP
Figure	14.2.14.1.1.2	Change from Baseline in PANSS Total Score by MIN-101 Plasma Concentration Quartiles	ITT (with PK)
Figure	14.2.14.1.2.2		ITT (with PK)
Figure	14.2.14.2.1.2	Change from Baseline in Marder Negative Symptoms	
			ITT (with PK)

